Neuropathic pain in SCI is common, impactful, and difficult to treat. Gabapentin is effective in the management of symptoms and concerns related to SCI including motor recovery, spasticity, and mood among others. This makes gabapentin an important pharmacologic intervention, which compels providers to define treatment guidelines related to its use. One aspect of which should relate to the timing of initiation of therapy. The goal of this study is to determine whether early initiation of treatment with gabapentin will decrease average pain scores and opiate use when compared to late initiation of treatment with gabapentin in the population with acute SCI. Gabapentin, although used commonly, is not started in all patients with acute SCI but is often started at the onset of neuropathic pain. If gabapentin is found to be more effective when initiated early, it would be reasonable to start gabapentin immediately following acute SCI in all patients in whom it is not otherwise contraindicated.

1. Objectives

- Primary

- To determine if the time from injury influences the prevalence of neuropathic pain in acute SCI
- To determine if the use of gabapentin in the early acute period influences the prevalence of neuropathic pain in patients with acute SCI
- To compare the efficacy of acute versus subacute initiation of gabapentin in treating neuropathic pain in SCI

- Secondary

- To compare the overall pain scores
- To determine the prevalence of neuropathic pain in those with SCI at admission and discharge to the inpatient rehabilitation hospital
- To compare the use of opiates
- To compare the average daily change in Functional Independence Measure (FIM)
- To compare the change in total motor score on the ASIA impairment scale
- To identify side effects of treatment with gabapentin and their frequency

2. Endpoints

Primary

- Presence of neuropathic pain at time of enrollment and again around time of discharge (Douleur Neuropathique 4, DN4)
- Neuropathic pain level (Neuropathic Pain Scale, NPS) at time of enrollment and again around time of discharge

Secondary

- Average pain level recorded in nursing flowsheet (Numeric Pain Rating Scale, NPRS)
- Weekly total use of opiates (total morphine milligram equivalents, MME)
- Change in FIM during rehabilitation
- Change in total motor score on the ASIA impairment scale during entire rehabilitation course

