- Side effects attributed directly to gabapentin in physician documentation and whether or not gabapentin was stopped due to these side effects

3. Design

- Prospective, observational, cohort, single center study
- The study will enroll subjects with acute spinal cord injury who are admitted to acute inpatient rehabilitation at MetroHealth Rehabilitation Institute (MRI).

- After enrollment, subjects will be followed through the end of their acute rehabilitation stay including any interruption in rehabilitation for which they require ED evaluation and/or acute hospital readmission so long as they return to MRI.
- Around the time of enrollment, subjects will be asked to complete the DN4 questionnaire and the NPS.
- Around the time of discharge, subjects will be asked to complete a second DN4 questionnaire and the NPS.
- The remainder of the data collection will be through review of the patient's electronic medical record (EMR).
- Patients will be divided into those who first received gabapentin during their acute inpatient hospitalization, prior to admission to acute rehabilitation, and those who did not. Additionally, the timing of gabapentin initiation will also be recorded.

4. Subject selection

- Study population

Subjects are patients who suffered acute spinal cord injury for which they are admitted to acute inpatient rehabilitation at MRI.
- Inclusion criteria

Subjects who meet all the following criteria may be given consideration for inclusion in this clinical investigation, provided no exclusion criterion is met

 1. Clinical diagnosis of acute spinal cord injury
 2. Admission to MRI for acute inpatient rehabilitation
- Exclusion criteria

Subjects who meet one or more of the following criteria will be excluded from this clinical study.

 1. Unable to communicate verbally or by writing, unable to follow basic instructions, or unable to answer questions regarding their symptoms

5. Subject Accountability

- Point of enrollment

The point of enrollment is the time at which time a subject signs and dates the valid, IRB approved informed consent form. No study-related procedure or assessments can take place until the informed consent form is signed.
- Withdrawal

All subjects enrolled to the study (including withdrawal or lost to follow-up) shall be accounted for and documented.

Reasons for withdrawal include:

 1. Physician discretion
 2. Subject choice
 3. Lost to follow up
 4. Death

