Subjects may withdraw from the study at any time, with or without reason without prejudice to further treatment.

6. Study methods

- Pre-screening

To determine eligibility for enrollment into the study, the inclusion and exclusion criteria must be assessed.

- Informed consent

After a patient has been identified as a potential candidate, based on meeting all inclusion and no exclusion criteria, written Informed Consent must be obtained by asking patients to read and review the valid IRB-approved Informed Consent. The informed consent process will abide by the MetroHealth Medical Center IRB process.

- Initial Visit

The initial visit will occur at or within 7 days of the time of enrollment and admission to rehabilitation

- o Visit Type: Visit to patient while they are admitted to hospital
 - Admission DN4 and NPS

- Final Visit

The final visit will occur at or within 7 days of the time of discharge from MRI

- o Visit Type: Visit to patient while they are admitted to hospital
 - Discharge DN4 and NPS

- Additional data collection: As outlined in Figure 2

The data collection will be completed via review of the EMR of each subject, and will include the following:

- o Demographics
 - Age
 - Sex
 - Race
 - History of drug use
 - History of smoking
- o Home pain medications prior to SCI injury
- o Date of injury
- o ASIA impairment scores (AIS; 1st documented AIS, rehabilitation admission AIS, and rehabilitation discharge AIS)
- o Operative vs nonoperative management of SCI
- o Length of stay in rehabilitation
- o Rehabilitation admission and discharge FIM scores
- o Rehabilitation admission and discharge total motor scores (TMS) as recorded on AIS
- o Pain scores (NPRS)
 - Average score per week from injury as documented in EMR
- o Opiate use
 - Total weekly MME per week from injury

- Side effects
 - Record side effects attributed to gabapentin by treating physician
 - Record if therapy was stopped and why (ineffective, no longer required, adverse reaction)

7. Statistical Analysis Plan

Subject demographics will be summarized by typical descriptive statistics to compare means or medians and measures of variability

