The relationship between the presence of neuropathic pain and: 1) the time from injury; 2) the timing of gabapentin initiation will be evaluated by building logistic regression models with dichotomous neuropathic pain (measured by DN4) as the dependent variable and time as the independent variable. Potential confounding variables will be added to the model if independently associated with the outcome of interest or based on theoretical grounds.

The efficacy of gabapentin by timing of initiation will be analyzed with a regression model with change in pain on the Neuropathic Pain Scale from admission to discharge with timing of gabapentin initiation as the independent variable. Potential confounding variables will be added to the model if independently associated with the outcome of interest or based on theoretical grounds.

8. Data analysis

- All enrolled subjects will be eligible for evaluation.

9. Data Safety/ Monitoring

The PI and co-investigators will monitor the progress of the research study, including assessments of data quality, participant recruitment, accrual and retention, subject's confidentiality, any adverse event(s), and external factors or relevant information that might have an impact on the safety or ethics of the study.

After recruitment, data analysis will occur and any changes to the risk/benefit ratio to study participation will be identified and reported to the IRB. In addition, the PI and co-investigators will meet on an annual basis and reports of the meeting will be submitted to the IRB.

If an adverse event occurs, it will be reported immediately to the MetroHealth Institutional Review Board (IRB). If an unexpected adverse event occurs, the investigators will assess the risk/benefit ratio of the study and submit any modifications deemed necessary to the IRB for approval. At the time of the IRB renewal, the PI will

submit information about the frequency of the monitoring, the dates that the monthly meeting took place, a summary of the cumulative adverse events, external factors or relevant information that might have an impact on the safety or the ethics of the study, and final conclusions regarding changes to the anticipated risk/benefit ratio to study participation and final recommendation related to the continuation, changing, or termination of the study.

10. Study Assessments

1. Assessment of presence of neuropathic pain (DN4) at time of admission and discharge

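### The only model for primary objective 3 measures NPS change from a baseline taken after the first gabapentin dose in every early-group patient, so it estimates differential change during rehabilitation, not acute versus subacute initiation

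*Combined protocol and SAP*

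**What the plan says.** Section 1 lists as a primary objective "To compare the efficacy of acute versus subacute initiation of gabapentin in treating neuropathic pain in SCI". Section 7 assigns efficacy by timing of initiation to a single model, a "regression model with change in pain on the Neuropathic Pain Scale from admission to discharge with timing of gabapentin initiation as the independent variable". The other models in section 7 are logistic models for presence of neuropathic pain on the DN4, which match the two prevalence objectives.

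Section 3 divides patients into "those who first received gabapentin during their acute inpatient hospitalization, prior to admission to acute rehabilitation, and those who did not", and also records when gabapentin was started. Section 7 does not say which form, group or time, enters the model.

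Section 6 sets the baseline: "The initial visit will occur at or within 7 days of the time of enrollment and admission to rehabilitation". Section 5 adds: "No study-related procedure or assessments can take place until the informed consent form is signed". Section 4 makes admission to the rehabilitation unit an inclusion criterion.

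Section 2 has as a primary endpoint "Neuropathic pain level (Neuropathic Pain Scale, NPS) at time of enrollment and again around time of discharge". NPS level is thus collected at both visits, but section 7 models only the change.

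**The concern.** A change score measures response to treatment when its baseline precedes treatment. Here it cannot do so in the early group, because the group is defined by exposure before the baseline visit. What early treatment achieved in the acute hospital lies inside the baseline and is subtracted from the result.

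Followed exactly, the model can show no effect, or a reversed one, when early initiation works. It can also exaggerate an early advantage if the groups differ at admission for other reasons. The Introduction says that gabapentin "is not started in all patients with acute SCI but is often started at the onset of neuropathic pain", so such differences are likely, and the comparison group can include patients who never receive the drug.

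The Introduction would use a positive finding to support starting gabapentin straight after acute injury in patients without a contraindication. A coefficient that mixes a timing effect with whatever was already present at admission should not carry that conclusion.

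**Working it through.** **Order of events.** In the early group: first dose (section 3), then rehabilitation admission (sections 3 and 4), then consent (section 5), then first NPS (section 6). No early-group patient can have a pre-dose NPS. In the comparison group, a patient who starts in rehabilitation before the first NPS, which the 7-day window allows, also has a post-dose baseline.

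**Inputs.** The documents give no effect size, SD, correlation or sample size, so there is no stated figure to reproduce. Every value below is assumed. Contrasts are early minus late; negative favours early.

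- Be, Bl: total benefit by discharge, early and late
- f: share of the early benefit gained before the admission NPS
- d: untreated gap at admission that does not persist
- s: severity gap that persists to discharge
- truth: -(Be - Bl)

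**Formulas** (late group untreated at the admission NPS).

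- Admission contrast = d + s - f·Be
- Discharge contrast = s - (Be - Bl)
- Change contrast = discharge - admission = f·Be - d - (Be - Bl)
- Adjusted for admission NPS, with within-group slope ρ: discharge - ρ·admission

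The persistent gap s cancels from the change contrast; f·Be and d do not.

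**Results.**

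| Assumed case | Truth | f = 0 | f = 1/3 | f = 2/3 | f = 1 |
|---|---|---|---|---|---|
| A. Be = 3, Bl = 2, d = s = 0; change = 3f - 1 | -1.0 | -1.0 | 0.0 | +1.0 | +2.0 |
| A, adjusted for admission NPS, ρ = 0.3; -1 + 0.9f | -1.0 | -1.0 | -0.7 | -0.4 | -0.1 |
| A, adjusted, ρ = 0.5; -1 + 1.5f | -1.0 | -1.0 | -0.5 | 0.0 | +0.5 |
| A, adjusted, ρ = 0.7; -1 + 2.1f | -1.0 | -1.0 | -0.3 | +0.4 | +1.1 |
| B. Be = Bl = 2, d = s = 0; change = 2f | 0.0 | 0.0 | +0.67 | +1.33 | +2.0 |
| C. As A, d = 2 (comparators arrive 2 points lower); change = 3f - 3 | -1.0 | -3.0 | -2.0 | -1.0 | 0.0 |

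Cases A and B err against early initiation. Case C errs in its favour for f below 2/3 and against it above.

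**Simulation.** With 200,000 patients per scenario, SD 20, within-patient correlation 0.6 and a 10-point early advantage at discharge, let 0, 5 or 10 points already be present at admission. The change coefficient was -10.06, -4.95 and +0.14. Adjusted for admission NPS it was -10.05, -6.94 and -3.85. The discharge-level difference was -10.02, -9.92 and -9.80.

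**Timing in days.** Let starts spread over days 1 to 35, with benefit k per day on drug and discharge on day 60. With the admission NPS on day 11, 18 or 25, the change model recovers 78%, 50% or 22% of the slope in discharge level. Among patients who start before the admission NPS it recovers none: both scores contain the same k per day of earlier start, and it cancels.

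**Never-users.** If half the comparators in case A are never treated, mean Bl = 0.5·2 + 0.5·0 = 1 and the discharge contrast becomes -(3 - 1) = -2.0. That is no longer the -1.0 between early and late starters. Neither model then answers the acute versus subacute question unless never-users are separated.

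**Limits of a discharge-level model.** It keeps s. If early starters are persistently 1 point worse, adjusting for a pre-dose score with correlation r leaves s·(1 - r): 0.7, 0.5 or 0.3 points for r = 0.3, 0.5 or 0.7. Both models can also err together:

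- Be = Bl = 2, f = 1/3, s = 1, r = 0.3: discharge 0 + 0.70 = +0.70, change +0.67, truth 0.
- Be = 3, Bl = 2, f = 2/3, s = 2, r = 0.3: discharge -1 + 1.4 = +0.4, change +1.0, truth -1.0.

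**The case against.** The best defence of the plan is that the change score is a reasonable choice in a non-randomised cohort. Treatment often follows pain onset, so stable severity differences are plausible; the change score cancels them and a discharge-level comparison does not. This stands, and is a reason to keep the change model.

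It can also be said that the documents never equate objective 3 with discharge NPS level. In the algebra above, truth is the discharge contrast when s = 0, so the discharge model is right by construction in cases A to C. The stated goal is whether "early initiation of treatment with gabapentin will decrease average pain scores and opiate use when compared to late initiation of treatment with gabapentin", which is closer to the secondary NPRS and MME endpoints, recorded weekly from injury. This also stands: discharge level is a second view, not the one correct target. But the goal is no closer to change after rehabilitation admission, and section 7 gives no model for NPRS or MME either.

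Two other defences do not repair the point. The general rule on adding confounders supplies no pre-dose NPS, and admission NPS is itself affected by treatment in the early group. The DN4 model addresses presence of pain, and section 7 does not say whether it uses the admission or the discharge assessment.

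A reader might infer that the model is biased against early initiation. The documents do not support a direction: case C shows the opposite error, and nothing in the plan fixes f, d or the benefits. A reader might also infer that a discharge model adjusted for first documented AIS and operative management would be free of the problem. Section 6 does not date either relative to gabapentin, and the Introduction discusses perioperative use, so they too may follow the first dose.

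**Conclusion.** The concern holds, and should be fixed before analysis. By the plan's own definitions, the baseline follows the first dose in every early-group patient. The coefficient measures differential change during rehabilitation; it equals the discharge contrast only when the groups do not differ at admission. Neither step depends on an assumed number.

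The size and net direction are unknown. The assumed cases show that a true 1-point early advantage can appear as anything from -3.0 to +2.0, depending on inputs that the documents do not give.

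A reader might go further and require the change and discharge models to agree before superiority is claimed. That is not supportable. In case A, the change model would block a true early advantage for every f of 1/3 or more, and in the two joint-error examples both models favour late initiation when it has no advantage. Nor does the point invalidate the study: NPS level is collected at both visits, so an admission gap can be seen and reported.

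**What to change.** Amend section 7 as follows.

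1. Keep the change model, but state that it measures change during rehabilitation and can be read as response to initiation only in patients whose first dose followed the admission NPS.
2. Add a model of discharge NPS level by timing of initiation, not adjusted for admission NPS. The main fit includes all patients and adjusts for age and pre-injury home pain medication. A further fit adds first documented AIS, operative management, and weekly NPRS and MME, each only where its date precedes the first dose. Report how many patients lack such values; they stay in the main fit.
3. Report NPS by group at admission and at discharge beside both models. Separate never-users from those who start during rehabilitation; they have no value if timing is entered as days to first dose.
4. Present both estimates for objective 3, each with its bias: the change model subtracts pre-admission benefit, and the discharge model keeps persistent severity differences and confounding by indication. State that neither alone, nor agreement between them, establishes early or late superiority.

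The cost is one more model, an amendment with IRB approval before implementation (section 11), and a more cautious conclusion. No new patient assessment is needed. The dates of the first AIS and of surgery are not on the section 6 list and would come from the same record review. NPRS measures overall rather than neuropathic pain, and patients who start in the first week from injury may have no pre-dose week, so the further fit will be weakest for the earliest starters.
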